## 2.4 STATISTICAL METHODS

In general, descriptive statistics of quantitative efficacy and safety endpoints (result and change from Baseline) by scheduled visit will be provided on observed cases (OC), ie, only including participants having a non-missing assessment at a specific visit.

Due to study early termination, the analyses specified in this document focus on demographics, disease characteristics at baseline, exposure, participant disposition, and safety. Primary and secondary efficacy data will be descriptively summarized.

### 2.4.1 Demographics and Baseline characteristics

Parameters described in [Section 2.1.1](#) will be summarized on the ITT population by randomized treatment group and overall using descriptive statistics.

Continuous data will be summarized using the number of available data, mean, SD, median, minimum, and maximum for each treatment group. Categorical and ordinal data will be summarized using the number and percentage of participants in each treatment group. Missing data will not be categorized in the summaries.

Technical formulas are described in [Section 2.5.1](#).

P-values on demographic and Baseline characteristic data will not be calculated.

## 2.4.2 Extent of investigational medicinal product exposure

The extent of IMP exposure will be assessed and summarized by actual treatment within the safety population ([Section 2.3.2](#)).

### 2.4.2.1 Extent of investigational medicinal product exposure

The extent of IMP exposure will be assessed by cumulative exposure (participant years), duration (days), and category (weeks).

Duration of IMP exposure is defined as last dose date – first dose date + 7, regardless of unplanned intermittent discontinuations (see [Section 2.5.3](#) for calculation in case of missing or incomplete data).

Duration of IMP exposure will be summarized descriptively as a quantitative variable (N, mean, SD, median, minimum, and maximum). Duration of treatment exposure will also be summarized categorically by numbers and percentages for each of the following categories: 1 to 2 weeks, 3 to 4 weeks, 5 to 8 weeks, 9 to 12 weeks, 13 to 18 weeks, 19 to 24 weeks, 25 to 30 weeks, >30 weeks. Cumulative duration of treatment exposure will be summarized similarly for  $\geq 1$  week,  $\geq 3$  weeks,  $\geq 5$  weeks,  $\geq 9$  weeks,  $\geq 13$  weeks,  $\geq 19$  weeks,  $\geq 25$  weeks, and >30 weeks. The duration of treatment exposure in weeks will be the duration (in days)/7 rounded up to the nearest integer.

## 2.4.3 Analyses of efficacy endpoints

Efficacy analyses will be performed on the ITT population using efficacy assessment collected during the study, including those obtained after IMP discontinuation or introduction of rescue therapy, unless otherwise specified (see [Section 2.5.4](#)).

A descriptive summary will be provided at screening, baseline, and Week 30, displaying observed value and change from baseline for efficacy endpoints (HbA1c, FPG, body weight, and % participants achieving 7%).

## 2.4.4 Analyses of safety data

The summary of safety results will be presented by treatment group on the “on-treatment period” as defined in [Section 2.1.4](#).

### *General common rules*

All safety analyses will be performed on the safety population as defined in [Section 2.3.2](#), unless otherwise specified, using the following common rules:

- Safety data in participants who do not belong to the safety population (eg, treated but not randomized) will be listed separately
- The potentially clinically significant abnormality (PCSA) values are defined as abnormal values considered medically important by the Sponsor according to predefined criteria/thresholds based on literature review and defined by the Sponsor for clinical

laboratory tests, vital signs, and ECG (PCSA version 3 date dated 21May2014 effective date 24May2014 [[Appendix A](#)])

- PCSA criteria will determine which participants had at least 1 PCSA during the on-treatment period, taking into account all evaluations performed during the on-treatment period, including nonscheduled or repeated evaluations. The number of all such participants will be the numerator for the on-treatment period PCSA percentage.
- The treatment-emergent PCSA denominator by group for a given parameter will be based on the number of participants assessed for that given parameter in the on-treatment period and by treatment group on the safety population.
- The analysis of the safety variables will be descriptive, and no systematic testing is planned.

#### **2.4.4.1 Analyses of adverse events**

##### ***Generalities***

The primary focus of AE reporting will be on TEAEs.

If an AE date/time of onset (occurrence, worsening, or becoming serious) is incomplete, an imputation algorithm will be used to classify the AE as pretreatment, treatment-emergent, or posttreatment. The algorithm for imputing date/time of onset will be conservative and will classify an AE as treatment emergent unless there is definitive information to determine it is pretreatment or posttreatment. Details on classification of AEs with missing or partial onset dates are provided in [Section 2.5.3](#).

Incidence tables will present AEs by SOC, HLGT, HLT, and PT, sorted in SOC internationally agreed order and HLGT, HLT and PT sorted alphabetically for each treatment group, and the number (n) and percentage (%) of participants experiencing an AE. Multiple occurrences of the same event in the same participant will be counted only once in the tables within a treatment phase. The denominator for computation of percentages is the safety population within each treatment group.

Sorting within tables ensures the same presentation for the set of all AEs within the observation period. For that purpose, the table of all TEAEs presented by primary SOC and PT sorted by the internationally agreed SOC order and decreasing frequency of PTs within SOCs will define the presentation order for all other tables unless otherwise specified. In case of equal frequencies of PTs within a SOC, the alphabetic order will be applied. Sorting will be based on the incidence in the efpeglenatide 6 mg group.

The internationally agreed order of SOCs shown below was described in the Introductory Guide MedDRA Version 19.1, September 2016 International Conference on Harmonisation for SOC:

1. Infections and infestations
2. Neoplasms benign and malignant (including cysts and polyps)
3. Blood and lymphatic system disorders

4. Immune system disorders
5. Endocrine disorders
6. Metabolism and nutrition disorders
7. Psychiatric disorders
8. Nervous system disorders
9. Eye disorders
10. Ear and labyrinth disorders
11. Cardiac disorders
12. Vascular disorders
13. Respiratory, thoracic, and mediastinal disorders
14. Gastrointestinal disorders
15. Hepato-biliary disorders
16. Skin and subcutaneous tissue disorders
17. Musculoskeletal, connective tissue, and bone disorders
18. Renal and urinary disorders
19. Pregnancy, puerperium, and perinatal conditions
20. Reproductive system and breast disorders
21. Congenital and familial/genetic disorders
22. General disorders and administration site conditions
23. Investigations
24. Injury, poisoning, and procedural complications
25. Surgical and medical procedures
26. Social circumstances
27. Product issues

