# 1 OVERVIEW AND INVESTIGATIONAL PLAN

## 1.1 STUDY DESIGN AND RANDOMIZATION

This is a Phase 3, multicenter, randomized, double-blind, placebo-controlled, 4-arm, parallel group study in participants with type 2 diabetes mellitus (T2DM) inadequately controlled with Metformin alone or in combination with sulfonylurea (SU).

After a Screening phase of up to 3 weeks (with a minimum of 10 days), participants will be centrally randomized (using permuted block randomization schedule) via Interactive Response Technology (IRT) in a 1:1:1:1 ratio to 1 of the following 4 treatment groups:

- Efpeglenatide 2 mg
- Efpeglenatide 4 mg
- Efpeglenatide 6 mg
- Efpeglenatide placebo

Randomization will be stratified by Screening hemoglobin A1c (HbA1c) (<8%, ≥8%) and SU use at screening (Yes/No). Participants will receive double-blinded treatment for 30 weeks. Additional details on the study design and plan is in [Section 1.4](#).

Approximately 640 participants (160 participants per treatment group) [details in [Section 1.3](#)] will be randomized.

The study was terminated early by the Sponsor on September 9, 2020 (hereinafter referred to as “early termination”).

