## 1.4 STUDY PLAN

This is a multicenter, 30-week, randomized, double-blind, placebo-controlled Phase 3 study consisting of 3 study periods:

- An up to 3-week screening period (with a minimum of 10 days)
- A 30-week double-blind, placebo-controlled treatment period, for efficacy and safety assessment
- A 6-week posttreatment follow-up period to collect safety information after last dose of IMP

The maximum study duration per participant will be 39 weeks. The graphical study design is shown in [Figure 1](#).

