#### ***Observation period***

The observation period will be divided into 3 main segments:

- The **pretreatment** period is defined as the time from informed consent up to the time of first injection of IMP
- The **on-treatment** period is defined as the time from the first injection of the IMP up to 30 days (7 days for hypoglycemia) after the last injection of the IMP
- The **posttreatment** period is defined as the period from the end of the whole on-treatment period

The **on-study observation** period is defined as the time from first injection of IMP up to either the last protocol-planned visit or the date of last available information if participants discontinue the study prematurely (ie, the date collected on e-CRF page “Completion of End of Study/Follow-up”), whichever is later.

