### 2.3.2 Safety population

The safety population is defined as:

- Randomized population who actually received at least 1 dose or part of a dose of the IMP, analyzed according to the treatment actually received.

In addition:

- Nonrandomized but treated participants will not be part of the safety population; however, their safety data will be presented separately
- Randomized participants for whom it is unclear whether they took the IMP will be included in the safety population as randomized
- For participants receiving 1 or more injections of efpeglenatide during the trial, regardless of being assigned to the efpeglenatide groups or not, the treatment group allocation for as-treated analysis will be included in the efpeglenatide dose group that they are exposed for longer duration. In case of a tie, the highest dose group will be used. Participants, who prematurely discontinued study treatment during the titration phase, will be summarized in their planned treatment group for as-treated analysis too.
- Randomized participants will be excluded from the safety population only if there is documented evidence (ie, all study dates recorded as no medication taken) that participants have not taken the study treatment. If a participant is dispensed double-blind IMP and is lost to follow-up without any documented evidence, the participant will be considered exposed.

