#### **2.4.4.2 Analysis of hypoglycemia**

Treatment-emergent hypoglycemia events will be tabulated separately from the AEs.

Event frequency and incidence of hypoglycemia events will be summarized by treatment for all reported hypoglycemia and per type of hypoglycemic event described in [Section 2.1.4.6](#) (ie, severe, documented symptomatic, asymptomatic, probable symptomatic, relative). Documented hypoglycemia (symptomatic or asymptomatic) will be also evaluated for the more stringent plasma glucose threshold of 3.0 mmol/L (<54 mg/dL), as well as for  $\geq 3.0$  and <3.9 mmol/L ( $\geq 54$  and <70 mg/dL), and  $\leq 3.9$  mmol/L ( $\leq 70$  mg/dL). Frequency and percentage of participants with at least 1 hypoglycemia event will be summarized as well.

Event rate of hypoglycemia per participant year will be calculated by treatment using the total number of hypoglycemia events from all participants (denoted as n) divided by the total exposures from all participants expressed in years (ie, participant exposure in days divided by 365.25, denoted as t). Multiple events from an individual participant will all count. Event rates of hypoglycemia per participant year (all reported hypoglycemia, severe, documented symptomatic, asymptomatic, probable symptomatic, relative hypoglycemia, and documented hypoglycemia with plasma glucose <3.0 mmol/L [ $< 54$  mg/dL], as well as for  $\geq 3.0$  and <3.9 mmol/L [ $\geq 54$  and <70 mg/dL], and  $\leq 3.9$  mmol/L [ $\leq 70$  mg/dL]) will be presented by treatment group for the on-treatment period.

A listing of participants for all severe hypoglycemia events reported on the specific eCRF “Hypoglycemic Event Information” page will be provided.

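### After the early stop, adverse events are still reported only as crude percentages of everyone dosed, although time at risk may vary widely; adding first-event rates would be a cheap improvement

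*SAP*

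**What the plan says.** SAP 1.1 plans 30 weeks of treatment and records: "The study was terminated early by the Sponsor on September 9, 2020". SAP 1.6 describes the document as a simplified plan for a synopsis report. SAP 2.4 turns the focus to baseline data, exposure, disposition and safety, with efficacy summarized descriptively.

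SAP 2.4.4.1 reports TEAEs, serious TEAEs, TEAEs leading to discontinuation, AESI and AERSM as number and percentage of participants, and sets the divisor: "The denominator for computation of percentages is the safety population within each treatment group". SAP 2.3.2 defines that population as "Randomized population who actually received at least 1 dose or part of a dose of the IMP", with no minimum exposure. Under SAP 2.1.4 the on-treatment period lasts "up to 30 days (7 days for hypoglycemia) after the last injection of the IMP".

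SAP 2.4.2.1 tabulates exposure separately, in participant-years, in days and in categories from 1 to 2 weeks up to more than 30 weeks. The one safety domain with an exposure-adjusted figure is hypoglycemia, in SAP 2.4.4.2: "Event rate of hypoglycemia per participant year will be calculated by treatment".

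**The concern.** A crude percentage estimates the risk over a stated period only if nearly everyone was observed for that period. When a sponsor stops a trial, late entrants contribute less time but count in full in the denominator. For events that keep occurring through treatment, the percentage then describes a mixture of follow-up times, and its distance from the full-period risk depends on how many participants were cut short and when.

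Safety is a main remaining output of this trial. Without a rate or a cumulative incidence, the percentages are hard to interpret on their own or to set beside a study with full follow-up.

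**Working it through.** The plan gives no adverse-event rate and no follow-up distribution, so there is no figure of its own to reproduce on this point.

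**Inputs from the documents.** Planned treatment: 30 weeks (SAP 1.1). Tail after the last injection: 30 days, so τ = 30/7 = 4.29 weeks (SAP 2.1.4). Denominator: the whole safety population (SAP 2.4.4.1).

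**Assumptions, not in the documents.** True 30-week risk R; constant hazard; a fraction f of participants truncated, with treatment time uniform on 0 to 30 weeks.

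**Step 1: the planned window.** Shortest, a single injection: 30 days. Longest, an injection at the Week 30 visit (Day 210): 210 + 30 = 240 days, or 34.3 weeks. The 6-week post-treatment follow-up (SAP 1.4) covers the tail unless a participant leaves early.

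**Step 2: the expected crude percentage.** Let x = −ln(1 − R) and λ = x/30 per week.

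- Full window: F = 1 − (1 − R)·exp(−λτ)
- Truncated participants, averaged over 0 to 30 weeks: T = 1 − exp(−λτ)·R/x
- Crude proportion: f·T + (1 − f)·F

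For R = 0.20: x = 0.2231, λ = 0.00744, exp(−λτ) = 0.9686 and R/x = 0.8963. Then F = 1 − 0.8 × 0.9686 = 0.225 and T = 1 − 0.9686 × 0.8963 = 0.132.

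| f | Crude % | Ratio to full window (22.5%) | Ratio to 30-week risk (20%) |
|---|---|---|---|
| 25% | 20.2 | 0.90 | 1.01 |
| 50% | 17.8 | 0.79 | 0.89 |
| 75% | 15.5 | 0.69 | 0.78 |
| 100% | 13.2 | 0.59 | 0.66 |

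For R = 5% the crude figures are 5.1, 4.5, 3.8 and 3.2%, against 5.7% over the full window. For R from 5% to 40%, the ratio to the full-window risk is 0.89 to 0.90 at f = 25% and 0.57 to 0.62 at f = 100%. The ratio to the 30-week risk is 1.00 to 1.02 and 0.65 to 0.68.

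**Step 3: early events.** Suppose all of the hazard falls in weeks 0 to 4. The 30-day tail exceeds 28 days, so even a participant with one injection is observed throughout: the ratio is 1.00. It would be 0.94 if observation ended at the last dose.

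**Step 4: arm comparisons.** With all arms truncated alike (f = 100%, no tail), a risk ratio of 2.00 becomes 2.04 for 20% against 10%, and 2.09 for 40% against 20%. With the tail, the first pair gives 13.2/6.5 = 2.03.

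**Step 5: what a first-event rate recovers.** Participants with an event divided by time to first event or censoring equals λ under a constant hazard, whatever the truncation. For R = 20%: 0.00744 × (365.25/7) × 100 = 38.8 per 100 participant-years, and 1 − exp(−30λ) returns 20%. For R = 5% the rate is 8.9.

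**The case against.** The strongest reply has four parts.

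1. **The tail and the unknown truncation.** A reader might equate follow-up with treatment time, take it to run from days to 30 weeks, and conclude that the percentages are about half of the true risk. Without the tail and with everyone truncated, 20% would indeed appear as 10.4%. The documents do not support this. They give a stop date but no enrolment dates, no number truncated and no follow-up range, and the adverse-event window adds 30 days after the last injection. This part stands and limits what can be claimed.

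2. **Early gastrointestinal events and arm comparisons are largely safe.** Protocol 2.3 describes nausea and vomiting as rising after the first injection and generally declining within about 2 to 4 weeks. Concurrent 1:1:1:1 randomization means that a sponsor stop should shorten all arms about equally. This also stands. If stops for intolerance differed by dose, time at risk for later events would differ too, but the documents do not show that this happened, and the early stop would not be its cause.

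3. **The contrast with hypoglycemia was planned.** Protocol Table 1 lists hypoglycemic events per participant-year and, separately, the number of participants with AEs. So this is no slip in drafting. The choice was made for a full-length trial, however, and the simplified SAP adds nothing for truncated follow-up.

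4. **Exposure and non-completion are already tabulated, and safety is descriptive.** This helps only in part. SAP 2.4.2.1 ends exposure 7 days after the last dose, whereas the adverse-event window ends 30 days after it, a mismatch of 30 − 7 = 23 days per participant. Nor does total exposure remove time after a first event. A reader can form only a rough rate, and a descriptive figure still needs a denominator that can be interpreted.

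**Conclusion.** The point holds as a cheap improvement. After the stop, the SAP reports adverse events only as crude percentages of everyone dosed, although time at risk may vary widely, and only hypoglycemia has an exposure-adjusted rate.

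The size is unknown. For a 20% 30-week risk, the shortfall against the full 30 weeks plus 30 days is about 10% of that risk if a quarter are truncated, and 41% if all are. This rests on a constant hazard, uniform truncation and the planned 30-day tail. Against the 30-week risk itself there is no shortfall when truncation is light, and essentially none for events confined to the first 4 weeks.

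A reader might infer that the percentages always understate 30-week risk, or that the arm comparisons are distorted. Neither follows. The effect is on absolute percentages of later-occurring events, and the SAP nowhere calls these percentages 30-week risks.

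**What to change.** In SAP 2.4.4.1, cover the TEAE overview rows, serious TEAEs, TEAEs leading to discontinuation, AESI and each AERSM group. Beside the crude percentage, give the number of participants with a first event per 100 participant-years at risk. Define time at risk as first injection to first event or end of the on-treatment period, whichever comes first, including the 30-day tail; the exposure duration of SAP 2.4.2.1 should not be used for this. State in the text and table footnotes that the crude percentages are not 30-week risks.

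Where events suffice, a Kaplan-Meier estimate may be added, with a note that it assumes independent censoring, which would be doubtful if intolerance drives stopping.

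The cost is a few columns. SAP 2.5.3 already sets rules for a missing last-dose date and for partial onset dates. The drawback is that a per-year rate assumes a roughly constant hazard, so it describes early-onset events poorly; for those the crude percentage should stay the main figure.

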### ***Analysis of all treatment-emergent adverse events***

The following TEAE summaries will be generated for the safety population.

- Overview of TEAEs, summarizing number (%) of participants with any
  - TEAE
  - Serious TEAE
  - TEAE leading to death
  - TEAE leading to permanent treatment discontinuation
  - Discontinued per investigator decision

- Discontinued per participant decision
- Treatment-related TEAE
- TEAEs of special interest (AESI)
- TEAEs requiring specific monitoring (AERSM)
- All TEAE by primary SOC, HLGT, HLT, and PT, showing number (%) of participants with at least 1 TEAE sorted by the SOC internationally agreed order. The other levels (HLGT, HLT, and PT) will be presented in alphabetical order. This sorting order will be applied to all other tables by SOC, HLGT, HLT, and PT, unless otherwise specified.
- Summary of common TEAEs (eg, PTs with incidence  $\geq 2\%$  in any treatment group) will be presented by primary SOC and PT.

***Analysis of all treatment emergent serious adverse event(s)***

- All serious TEAEs by primary SOC, HLGT, HLT, and PT, showing the number (%) of participants with at least 1 serious TEAE.

***Analysis of all treatment-emergent adverse event(s) leading to treatment discontinuation***

- All TEAEs leading to treatment discontinuation per investigator decision, by primary SOC, HLGT, HLT, and PT, showing the number (%) of participants
- All TEAEs leading to treatment discontinuation per investigator and/or participant decision, by primary SOC, HLGT, HLT, and PT, showing the number (%) of participant.

***Analysis of adverse events of special interest (AESI) and requiring specific monitoring (AERSM)***

TEAEs of special interest (AESI) and requiring specific monitoring (AERSM) include AE defined in [Section 2.1.4](#) and the criteria of AESI and AERSM are in [Table 1](#).

**Table 1 - Criteria for AESI and AERSM**

AE Grouping	Criteria
AESI	
Pregnancy	"Pregnancy" or "Partner pregnancy" checked
Symptomatic Overdose	"Overdose" checked" and symptomatic (AEOVSYP) ="Yes"
Increase in ALT >3ULN	"ALT Increase" checked and Yes to the question "Is the event an AESI?" in eCRF form "Adverse Events"
AERSM	
Severe GI events	AE severity= "severe" using Gastrointestinal disorders CMQ
Severe hypoglycemia	Any hypoglycemia event which required assistance (from hypoglycemia page)
Pancreatic events	Cases reported in eCRF "Suspected or confirmed Pancreatitis" page or AE category = "Pancreatic Neoplasm"

AE Grouping	Criteria
Selected cardiovascular event	
Cases reported in the following specific eCRF pages:
 
 
• “Suspected or confirmed MI/Unstable Angina”
 
• “Suspected or confirmed cerebrovascular event”
 
• “Suspected or confirmed heart failure” led to unplanned hospitalization, led to urgent/unscheduled visit to emergency room or an urgent/unscheduled outpatient heart failure treatment unit, or infusion center, or office/practice visit, not followed by hospitalization, or occurred while patient was hospitalized for another reason
 
• Primary cause of death in eCRF “Death (CV)” as Acute MI, Sudden cardiac death, Heart failure or cardiogenic shock, Stroke, Complication of cardiovascular procedure, Other cardiovascular cause, or Undetermined cause of death
 

Calcitonin and thyroid C-cell neoplasm	
Using Calcitonin increase CMQ
 
Using Medullary thyroid cancer CMQ

Acute renal failure	Using Acute renal failure CMQ
Severe injection site reaction	Intensity = "Severe" + Using Injection site reaction_ CMQ.
Severe allergic reactions	Intensity = "Severe" + CMQs for anaphylactic reaction, angioedema, severe cutaneous adverse reaction, anaphylactic/anaphylactoid shock conditions (under SMQ "Shock"), and hypersensitivity.
Severe immune complex disease	Intensity = "Severe" using Immune complex disease CMQ
Diabetic retinopathy complications	Cases reported in eCRF “Diabetic Retinopathy Complementary Form”

The following TEAE summaries will be generated for the safety population:

- All AESI by prespecified grouping and PT, showing number (%) of participants with at least 1 AESI, with PTs sorted by decreasing order in Efpeglenatide 6 mg group
- All AERSM by prespecified grouping and PT, showing number (%) of participants with at least 1 AERSM, with PTs sorted by decreasing order in Efpeglenatide 6 mg group.

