An AE requiring specific monitoring is a serious or nonserious AE of scientific and medical concern specific to the Sponsor's product or program, for which ongoing monitoring may be appropriate. Such events may require further investigation to characterize and understand them. These events should be reported on the AE page and additional information required on the specific eCRF page (where applicable) and will only qualify for expedited reporting when serious (fulfilling SAE criteria).

The AEs requiring specific monitoring for this study are as follows:

- Severe GI events
- Severe hypoglycemia (see [Section 8.2.5](#))
- Pancreatic events (including abnormal values of pancreatic enzymes [see Appendix 7, [Section 10.5.2](#)]) – will be adjudicated by CEC
- Major adverse cardiovascular events (MACE; CV death, myocardial infarction, stroke) and other specific CV events (eg, heart failure leading to hospitalization) – will be adjudicated by CEC
- Calcitonin increase >5.9 pmol/L (20 pg/mL) and thyroid C-cell neoplasm (see Appendix 7, [[Section 10.5.3](#)])
- Acute renal failure (see Appendix 5 [[Section 10.5](#)] for definition)
- Diabetic retinopathy complications (will be reviewed by an independent ophthalmologist expert; see Appendix 1 [[Section 10.1.4.3](#)]); a written report from professional eye care provider will be required
- Severe injection site reaction
- Severe allergic reactions
- Severe immune complex disease

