In the presence of clinical signs and/or symptoms evocative of pancreatitis (as previously described) associated with elevated amylase and/or lipase, treatment with the IMP should be promptly and at least temporarily discontinued pending further clinical evaluation and diagnosis confirmation. Clinical signs and/or symptoms are to be documented in the source data.

A laboratory determination of amylase and lipase must be obtained at the time of the event and again within 48 hours or earlier as clinically indicated. If the value(s) remain(s) >2 × ULN, then amylase and/or lipase levels should be retested as described in [Section 10.5.2.1](#), or more often if clinically indicated.

A gastroenterologic evaluation and imaging (ultrasound and/or CT or MRI with contrast, as appropriate) must be performed as clinically indicated and as per clinical practice and local guidelines. If a diagnosis of pancreatitis is confirmed, IMP should not be restarted and should be permanently discontinued.

In both cases as previously described ([Section 10.5.2.1](#) and [Section 10.5.2.2](#)), all laboratory or clinical documentations must be collected. If the retest confirms lipase and/or amylase values are >2 ULN, the event must be reported in the eCRF on the specific AE form and the specific complementary forms, using the appropriate verbatim, eg, “increased amylase and/or lipase” in case of isolated enzyme elevation, “suspected pancreatitis” in the presence of clinical signs evocative of pancreatitis if the diagnosis is suspected but cannot be confirmed or excluded, and “pancreatitis” if the diagnosis has been confirmed.

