#### **2.1.4.1 Adverse events observation period**

The AE observations will be classified per the observation periods of safety data as defined above into the following:

- **Pretreatment AEs** are AEs that developed or worsened or became serious during the pretreatment period
- **Treatment-emergent AEs (TEAEs)** are AEs that developed or worsened or became serious during the on-treatment period
- **Posttreatment AEs** are AEs that developed or worsened or became serious during the posttreatment period

All AEs (including serious adverse events (SAE), AESIs, and AEs requiring specific monitoring) will be coded to a lower-level term (LLT), preferred term (PT), high-level term (HLT), high-level

group term (HLGT), and associated primary system organ class (SOC) using the version of MedDRA currently in effect at the time of database lock.

Adverse events of special interest (AESI) include the following terms:

- Pregnancy of a female participant entered in a study as well as pregnancy occurring in a female partner of a male participant entered in a study with IMP/NIMP
- Symptomatic overdose (serious or non-serious) with IMP/NIMP
- Increase in alanine aminotransferase (ALT) >3 x upper limit normal (ULN)

Adverse events requiring specific monitoring (AERSM) include the following terms:

- Severe gastrointestinal (GI) events
- Severe hypoglycemia
- Pancreatic events (including abnormal values of pancreatic enzymes, pancreatitis and pancreatic neoplasm)
- Selected cardiovascular events (CV death, MI, stroke, heart failure leading to hospitalization, unstable angina, and transient ischemic attack [TIA])
- Calcitonin increase >5.9 pmol/L (20 pg/mL) and thyroid C-cell neoplasm
- Acute renal failure
- Diabetic retinopathy complications
- Severe injection site reaction
- Severe allergic reactions
- Severe immune complex disease

Independent Clinical Endpoint Committee(s) (CEC) will review, assess, and/or adjudicate all events of death, selected CV events and pancreatic events.

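### SAP Table 1 gives abnormal pancreatic enzyme values no explicit route into the pancreatic row of the AERSM table, although SAP 2.1.4.1 and protocol 8.3 define them as pancreatic events

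*SAP*

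**What the plan says.** SAP 2.1.4.1 lists among the AERSM "Pancreatic events (including abnormal values of pancreatic enzymes, pancreatitis and pancreatic neoplasm", which is three components. Protocol 8.3 agrees on the enzyme component, "Pancreatic events (including abnormal values of pancreatic enzymes", and refers the reader to protocol 10.5.2 for it.

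For the analysis, SAP 2.4.4.1 says that "the criteria of AESI and AERSM are in" Table 1. The pancreatic row of that table selects cases on the "Suspected or confirmed Pancreatitis" eCRF page, or AEs in the Pancreatic Neoplasm category. The resulting output is "All AERSM by prespecified grouping and PT, showing number (%) of participants with at least 1 AERSM".

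Protocol 10.5.2.2 covers lipase and/or amylase values confirmed above 2 x ULN on retest, with or without symptoms: "the event must be reported in the eCRF on the specific AE form and the specific complementary forms, using the appropriate verbatim". It then gives three verbatims. One applies "in case of isolated enzyme elevation", one to suspected pancreatitis and one to confirmed pancreatitis. The complementary forms are not named.

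**The concern.** The definition has three components and the selection rule explicitly reaches two of them. A programmer who follows Table 1 as written would not select an AE of increased lipase or amylase unless the site had also completed the pancreatitis page. The pancreatic row, and the AERSM line in the TEAE overview that rests on the same criteria, could then report fewer participants than the SAP's own definition implies.

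This matters because protocol 10.5.2 asks for close monitoring of pancreatitis and pancreatic enzymes as a class issue. After early termination, the simplified SAP is mainly a safety document. The AERSM table is where a reader would look for a by-arm count of pancreatic events.

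**Working it through.** No arithmetic applies. The check is a comparison of the definition, the reporting route and the selection rule.

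| Component (SAP 2.1.4.1) | AE verbatim (protocol 10.5.2.2) | Route into the pancreatic row (SAP Table 1) |
|---|---|---|
| Abnormal enzyme values | Its own verbatim, for isolated elevation | None stated |
| Pancreatitis | Suspected pancreatitis, or pancreatitis | Pancreatitis eCRF page |
| Pancreatic neoplasm | Not covered in 10.5.2 | Pancreatic Neoplasm AE category |

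1. **Does the page title cover an isolated rise?** Not on its face. The title matches the second and third verbatims of protocol 10.5.2.2, not the first.

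2. **Could the enzyme component enter another way?** Only if the pancreatitis page is one of the complementary forms that protocol 10.5.2.2 requires. The documents neither confirm nor exclude this.

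3. **Is leaving out enzyme terms a convention of Table 1?** It does not look like one. Calcitonin increase, the comparable laboratory-based AERSM, has its own CMQ in the same table. Where Table 1 relies on a complementary form, as for diabetic retinopathy, it names the form.

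4. **Where else would a confirmed rise appear?**
   - It must be reported as an AE, so a treatment-emergent case falls in the all-TEAE table by SOC, HLGT, HLT and PT (SAP 2.4.4.1). It also falls in the common-TEAE table if its PT reaches the cut-off, for which the SAP gives 2% in any group as an example.
   - Pancreas-related events sent to the CEC are listed (SAP 2.4.4.1, adjudicated events).
   - SAP 2.1.4.3 names amylase and lipase and says laboratory values will be summarized. SAP 2.4 provides descriptive statistics by visit for quantitative safety endpoints.
   - Appendix A sets a PCSA limit of 3 x ULN or more for both enzymes, which differs from the protocol's reporting trigger of above 2 x ULN. SAP 2.4.4 has no laboratory subsection, and the only PCSA summary given its own description is for heart rate.

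5. **Do these replace the missing count?** No. The TEAE tables do not group these terms as pancreatic events, the adjudication output is a listing, and laboratory summaries do not count AEs. They do keep the events visible.

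**The case against.** The strongest reply concerns the eCRF. Protocol 10.5.2.2 makes the complementary forms mandatory, so capture is not left to a site's choice. The only pancreas-specific page named in either document is the pancreatitis page. If that page is the required form, Table 1 already selects every confirmed rise and only the wording is incomplete. This stands as a possibility. It does not remove the point, because the SAP should state the rule and the page title does not describe an isolated rise.

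A second reply is that this is a simplified SAP for a synopsis report, with descriptive safety analysis and no systematic testing planned. No test or decision rule depends on the row. That is correct and limits the weight of the point.

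A reader might go further and infer that enzyme rises disappear from safety reporting, that sites will differ in which form they use, or that most of the pancreatic category would be missing. The documents support none of these. The events remain in the TEAE tables, no competing form is named, and no rate is given for enzyme rises, pancreatitis or neoplasm. Applying an assumed rate to 160 per arm would not help either: that is the planned size of a trial that the sponsor stopped early.

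**Conclusion.** The mismatch is real: Table 1 as worded does not deliver the definition in SAP 2.1.4.1. The consequence is conditional. If the pancreatitis page is not the complementary form for isolated elevations, a retest-confirmed isolated rise above 2 x ULN reported as an AE is left out of the by-arm pancreatic row. If it is that form, the rise is counted and only the statement of the rule is missing.

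In the first case the grouped count is incomplete, but the signal is still reported elsewhere. The number of participants affected cannot be derived from the documents. The conclusion rests on reading Table 1 literally and on the eCRF, which is not available here. It does not depend on any assumed event rate.

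**What to change.** Extend the pancreatic row of Table 1 with a third route: AEs of increased lipase and/or amylase reported under protocol 10.5.2, identified by a preferred-term list or a CMQ as for calcitonin. Since the table is presented by PT, enzyme rises can be shown separately from pancreatitis and neoplasm within the row. If the pancreatitis page is in fact the form for isolated rises, say so in the same row.

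A criterion based on raw laboratory values is not recommended. A value without an AE record has no PT and does not fit this table.

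The cost is a short SAP edit and a term list, with no new data. There are two downsides. The pancreatic-event count may be larger and must be read by component. A term-based rule may also admit some rises reported as AEs without retest confirmation, which a footnote to the table can state.
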